1.0 Study Summary

Study Title	Assessment of Sous Vide Water Baths for Acute Rewarming of Frostbitten Extremities
Study Design	Patients with acutely frostbitten hands or feet presenting to the emergency department will be consented to participate in the study. An ANOVA sous vide device will be attached to a water basin and set at 38°C. Two thermometers will continuously monitor water bath temperatures and the readings from the thermometers and sous vide device will be recorded every two minutes. The frostbitten extremity will remain in the circulating warm water bath for 30 minutes, at which time the extremity will be evaluated to see if rewarming is complete (warm to touch, pliable tissue). Tissue that is still frozen will be placed back into the water bath for an additional 30 minutes, at which time they will be reassessed. Medical providers directly involved in the care of the patient will fill out a survey regarding viability of this method and ease of use.
Primary Objective	To assess the ability of sous vide rewarming in maintaining constant water bath temperatures and efficacy in rewarming the acutely frostbitten extremity.
Secondary Objective(s)	To determine the ease of use of sous vide water bath rewarming in the acutely frostbitten extremity.
Research Intervention(s)/ Invest. Agent(s)	ANOVA Precision® Cooker sous vide device
IND/IDE #	NA
Study Population	Patients presenting to the emergency department with acute frostbite requiring rewarming; Providers to conduct rewarming, and complete a survey
Sample Size	1-5 patients locally, with anticipation of multicenter collaboration at 5-10 additional locations with similar enrollment goals.
Study Duration for individual participants	1-2 hours
Study Specific Abbreviations/ Definitions	SVD – sous vide device, SVR – sous vide rewarming

PROTOCOL TITLE: Assessment of Sous Vide Water Baths for Acute Rewarming of Frostbitten Extremities.

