4.0 Study Endpoints*

- The primary study endpoint will be the rewarming of frostbitten extremities for 30 minutes at 38°C.
- The secondary study endpoint will be a survey regarding ease of use of this rewarming modality.
- The primary safety endpoint will be patient pain or discomfort that is determined to be unrelated to the discomfort known to be associated with rewarming frostbitten tissue. Two consecutive temperature measurements above 42°C will prompt the cessation of the SVR.

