6.0 Procedures Involved*

- Patients presenting to the ED at Dartmouth-Hitchcock and external study sites with acute frostbite (tissue still frozen) of the hands and/or feet will be identified and approached for recruitment. Patients not entering the study will continue to be treated by ED providers in the traditional fashion.
- Patients recruited for the SVR study will be consented to have their circulating warm water bath(s) heated by the novel SVR method. Providers or nurses caring for the study subjects will be consented to participate and will 1) conduct the SVR procedure, and 2) complete a questionnaire. A researcher will gather SVR equipment and attach two thermometers on the basin: one on the side nearest the SVD, the other on the opposite side. The researcher will verbally walk the provider or nurse carrying out the SVR through the following steps. A 15 L Sterilite® basin will be filled to the marked line (12cm) with water from jugs at room temperature, for each frozen extremity. One extremity can be rewarmed in a single basin, with the possibility for up to four simultaneous SVR basins for a patient with frostbite of all hands and feet. The SVD will be attached to the distal edge of the basin, with one SVD per rewarming basin. The SVD will be turned on and set to maintain the bath at a constant 38°C for 30 minutes duration. The thermometers will be powered on continuously and the researcher will record temperatures simultaneously from each thermometer and the SVD every 2 minutes. At the end of the 30 minute treatment, the extremity will be assessed by the researcher for warmth and pliability. If the extremity still feels cold or frozen, an additional 30 minutes in the water bath will commence, with

PROTOCOL TITLE: Assessment of Sous Vide Water Baths for Acute Rewarming of Frostbitten Extremities.

subsequent reassessment. Rewarming will be considered complete when the affected tissue becomes red or purple, soft, and pliable.

- Patients who do not consent to SVR and elect for traditional water bath management will be asked for their consent to record the similar demographic, water temperature, and time-to rewarm data as in the SVR treatment arm. After re-warming is complete, the provider will be asked to fill out a survey regarding the ease of use and efficacy of the SVR.
- *Describe:*
 - *Procedures performed to lessen the probability or magnitude of risks.*

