 - The blood pressure cuff used in the standard emergency department assessment of vital signs will be placed on an extremity that is not currently being rewarmed, whenever possible, to avoid constricting blood flow to the affected tissue.
- *Data Collection:*
 - Prior to rewarming, physical examination of the patient, including the frozen extremity, will be completed and documented in the EPIC/EMR chart by the provider.
 - Two thermometers, placed in the rewarming basin, will continuously monitor the water temperature. The temperature reading on both thermometers as well as the SVD will be recorded on a paper data sheet by a trained provider at 2-minute intervals until the 30 minutes of treatment are complete.

PROTOCOL TITLE: Assessment of Sous Vide Water Baths for Acute Rewarming of Frostbitten Extremities.

- The researcher will repeat an exam, assessing all extremities being treated by SVR, at 30 minutes to determine warmth and pliability of the tissue, confirming thaw. Rewarming will be considered complete if the affected tissue becomes red or purple, soft, and pliable. The same rewarming criteria applies for all extremities.
 - The provider will be asked to fill out a survey on all acute frostbite patients whom consent to the study protocol, as well as those that do not.
 - *The source records that will be used to collect data about subjects. (Attach all surveys, scripts, and data collection forms.) If there are plans for long-term follow-up (once all research related procedures are complete), what data will be collected during this period.*
 - The patient's age and sex will be recorded. The physical examination and pertinent medical information will be reviewed to confirm the location and extent of the frostbite and for contributing conditions.
 - Demographics and relevant medical history will be accessed.
 - Please see attached surveys and data collection forms.
 - Enrolled subjects may be contacted via phone and myDH or local electronic medical record communication at 6 months post-enrollment to assess long term outcomes of their frostbite. Chart review to assess related complications will also occur at this time.
 - *Explain if any part of this study involves genetic analysis of biological specimens. If yes, explain whether the study is based on one the following:*
 - This study does not involve genetic analysis of biological specimens.

Provider Participation:

- *Role/Activities:*

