PROTOCOL TITLE: Assessment of Sous Vide Water Baths for Acute Rewarming of Frostbitten Extremities.

- Providers assigned to a patient in the emergency department who is determined to have acute frostbite will be targeted.
- The provider's role will be to identify an acute frostbite patient and ask their patient whether they would be interested in hearing more about and potentially participating in a study assessing a new way to rewarm their frostbitten tissue.
- If the patient agrees, the provider access the study on-call investigator list (posted in the ED provider area) and inform a researcher of the patient and need to discuss the stud and potentially enroll the patient.
- *Recruitment:*
 - Providers assigned to a patient in the emergency department who is determined to have acute frostbite.
- *Eligibility:*
 - Any provider managing a frostbite patient at the training levels of PA, APRN, resident physician, fellow, or attending physician are eligible.
- *Consent Process:*
 - Once the patient has consented to participate, the provider will be consented in an area of the emergency department separate from the patient's room, using the provider consent form.
- *Risks/Benefits:*
 - Risks to providers should be minimal. We do not anticipate providers having any difficulty with voluntary decision-making for this study.
 - Benefits to the provider may include improved work flow due to the decreased labor in maintaining a SVR water bath in comparison to manual water bath management. Additionally, participation will provide a firsthand opportunity to treat acute frostbite with a new modality that has potential for increased use in the future.
- *Data Collection:*
 - After successful completion of the SVR, providers will be asked to take a short, 6-question paper survey regarding ease-of-use of the SVR.

PROTOCOL TITLE: Assessment of Sous Vide Water Baths for Acute Rewarming of Frostbitten Extremities.

- Paper data collection forms will be kept in a locked office until transferred by the PI to a Microsoft excel file on a password-protected DH computer.

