10.0 Inclusion and Exclusion Criteria*

- The primary and sub-investigators will identify patients presenting to the emergency department with a chief complaint of frostbite, as seen on the EMR patient tracking board. Reminder signs and group awareness in the emergency department of this study will help alert providers of the potential to approach subjects for enrollment who presented to the department with an associated complaint, such as “foot pain” or other chief complaint, but determined to have acute frostbite on initial examination. The PI or a Sub-I will be on-call to drive to the ED to enroll and consent the patient with the standard forms, and assist with the treatment. Consent will always be obtained in-person, by a study team member with consenting privileges.
Inclusion criteria: Age 18 or up or <17 with parent or guardian able to provide consent, ability to understand English and provide consent to the study, acute frostbite (frozen tissue) of the hands or feet.
- *Exclusion criteria:* Children under age 18 without parent or guardian, frostbite that has already thawed, frostbite (thawed or acute) of tissue other than hands or feet, inability to understand English and to provide consent.
- *Indicate specifically whether you will include or exclude each of the following special populations: (You may not include members of the above populations as subjects in your research unless you indicate this in your inclusion criteria.)*
 - *Adults unable to consent* - Exclude
 - *Individuals who are not yet adults (infants, children, teenagers)* - Include
 - *Pregnant women* - Include
- *Prisoners* - Exclude

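### The ease-of-use survey measures use with a researcher at the bedside, and the plan leaves open who records temperatures and whether study-team members may rate

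*Combined protocol and SAP*

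**What the plan says.** Section 4.0 defines the endpoint: "The secondary study endpoint will be a survey regarding ease of use of this rewarming modality". The Study Summary gives the matching objective: "To determine the ease of use of sous vide water bath rewarming in the acutely frostbitten extremity". Neither says whether assisted or unaided use is meant. Section 2.0 makes ease of use part of the hypothesis.

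Section 6.0 describes the use that is rated. It begins "A researcher will gather SVR equipment and attach two thermometers on the basin" and continues "The researcher will verbally walk the provider or nurse carrying out the SVR through the following steps". The provider or nurse who is talked through the steps then answers the questionnaire. Section 10.0 sets out the duties of the principal investigator or a sub-investigator in these words: "on-call to drive to the ED to enroll and consent the patient with the standard forms, and assist with the treatment".

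On recording, the procedural text of Section 6.0 says "the researcher will record temperatures simultaneously from each thermometer and the SVD every 2 minutes". The Data Collection text of the same section says the readings are "recorded on a paper data sheet by a trained provider at 2-minute intervals". Section 17.0 has the forms completed by clinicians or investigators.

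On who may rate, the Provider Participation text of Section 6.0 says "Any provider managing a frostbite patient at the training levels of PA, APRN, resident physician, fellow, or attending physician are eligible". It contains no exclusion for study-team members.

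**The concern.** A provider's rating of a device reflects everything that happened during its use. Here that includes a researcher who brings the equipment, fits the thermometers and explains each step. A favourable score could reflect the device, the coaching, or both, and the planned summary does not separate them.

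This matters because the rationale reaches further than the setting that is tested. Section 3.0 argues that such a device would reduce provider effort and improve care in remote places without reliable hot water. Such settings would not normally have a study investigator at the bedside. If the paper concludes simply that the device is easy to use, readers may carry the finding to places where it was not studied.

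Two loose ends add to this. If some raters also make the 2-minute recordings and others do not, they rate different workloads, and part of that workload exists only because of the research. If a study-team member happens to be the treating provider, nothing in the eligibility text stops that person from rating the device under study.

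**Working it through.** The plan gives no sample size calculation, power or significance level (Section 12.0 calls it a feasibility study), so there is no stated figure to reproduce. The check compares the sections and adds a simple count.

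**1. Who does what in the rated use (Section 6.0, procedural text).**
- Researcher: gathers equipment, attaches two thermometers, explains each step, assesses the limb at 30 minutes.
- Provider or nurse: carries out the procedure under that guidance, which covers filling the basin, attaching the device and setting it, then completes the survey.
- PI or Sub-I: comes in to obtain consent and helps with treatment (Section 10.0).

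The rated use is therefore supported use, although the provider still operates the device.

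**2. Who records temperatures.**
- Section 6.0, procedural text: the researcher.
- Section 6.0, Data Collection: a trained provider.
- Section 17.0: clinicians or investigators.

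These can be made to agree if the trained provider is a study-trained researcher, but the text does not say so, and Section 17.0 allows either role.

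**3. Size of the recording task.** Inputs from Section 6.0: every 2 minutes, 30 minutes, 3 instruments (two thermometers and the device), up to four basins.
- Time points: 30 / 2 = 15, or 16 if a reading at time 0 is included (the plan does not say).
- Per basin: 15 × 3 = 45, or 16 × 3 = 48.
- Four basins, the maximum: 45 × 4 = 180, or 48 × 4 = 192.

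This counts a task whose owner is unclear. It does not measure bias.

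**4. Who may rate.** The eligibility text admits any managing provider at the listed levels. Section 13.0 lists the PI and Sub-Is together with other providers, so an investigator could also be a treating provider. Against this, Section 6.0 has the provider call the on-call investigator, and Section 21.0 has the researcher approach the provider for consent. Both describe two people.

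For scale only, assume one survey per case and a single study-team rater:
- With the 5 to 20 cases in Section 2.0: 1/20 = 5% to 1/5 = 20% of responses.
- With the Study Summary (1 to 5 local patients plus 5 to 10 further sites with similar goals): the total is 1 + 5 × 1 = 6 to 5 + 10 × 5 = 55, so 1/55 = 1.8% to 1/6 = 16.7%.

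This too is a share of responses, not an estimate of bias.

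**5. What the analysis does with it.** Section 17.0 plans descriptive statistics for ease of use and does not mention help given or who recorded. Its description of the collection form covers identifiers, the temperature table and adverse events. The survey and the form are attachments that are not in the supplied text, so an item on assistance cannot be ruled out.

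**The case against.** The strongest reply is that the protocol never claims to measure unaided use. It is a small feasibility study with descriptive analysis, and guiding staff through early clinical use of a device not approved for medical use is reasonable and openly described. That stands. The problem is an endpoint left undefined on this point, not a contradiction with a stated one.

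It can also be said that the researcher does not set up the whole procedure. That stands too: the provider or nurse still does the filling, attaching and setting. Handling of the thermometers by the researcher arguably keeps study monitoring out of the rating.

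On recording, Section 24.0 gives everyone assisting with the research one-on-one training, so the trained provider may be study staff. This is plausible, and a load on the rater is not established. It is only left open.

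A reader might infer that investigators are planned to rate their own device. The documents do not support that. No section plans it, and the workflow separates the roles; the eligibility text merely fails to rule it out. A reader might also infer that coaching or self-rating raises the score and that recording lowers it. The documents give no evidence on either effect, so no direction should be claimed.

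What survives is that the plan, followed as written, could report the device as easy to use without saying that the ease was rated under researcher support.

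**Conclusion.** The point holds in a limited form. The ease-of-use result will describe use with an investigator on site, and by itself it cannot carry the wider claim about provider effort or remote use. That follows from the coaching alone. It is also unclear whether the rater may carry 45 to 48 research readings per basin, and study-team members are not barred from rating.

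The count assumes the 2-minute schedule over a single 30-minute treatment. The size and direction of any effect on the score are unknown. The primary endpoint is not affected. This is a cheap improvement of minor severity.

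**What to change.** Keep the researcher at the bedside and make four changes.

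1. Reconcile the two statements in Section 6.0 and the one in Section 17.0, so that one named study role, other than the survey respondent, records the temperatures.
2. State in the Provider Participation text that the PI and Sub-Is do not complete the survey, or that their responses are reported separately.
3. If the attached forms lack it, add a short record for each use showing which steps (basin filling, thermometer placement, attaching and setting the device, monitoring) were done unaided, done with prompting, or done by the researcher. Report ease of use alongside it.
4. Describe the endpoint and the result as ease of use with researcher support.

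The cost is some protocol wording, a few tick boxes, an occasional lost survey when an investigator is the treating provider, and a narrower claim. The record of help is best made at the time of use, because it cannot be reliably reconstructed later.

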3.0 Background*

- Frostbite is a clinical entity in which extremities, digits, and appendages undergo freezing damage due to exposure to environmental cold. Once in a safe environment where the potential for re-freezing is minimal, the current standard of care for acute frostbite is the rapid rewarming of the affected body part, using a circulating warm water bath targeted to 37-39°C. There is no current “best” modality to warm and circulate the water. Depending on resources, this may be difficult and time consuming. In the field, water can be heated over a fire and added to a water bath. If heated water is present, hot tap water can be incrementally added to a water bath to achieve and maintain the targeted temperature. In the ED, some have advocated for placing the frostbitten hand or foot in a sink with running hot water and a thermometer in the sink to detect temperature. These methods are difficult at best, and may be dangerous in that they either do not maintain the water at the targeted temperature, or burn the frostbitten and often insensate extremity. An inexpensive, small, and transportable device that could reliably heat and circulate the water would decrease provider effort and optimize the water bath to the targeted temperature range. In remote locations where electricity is present but not reliably hot water, a portable heating device would drastically improve care.
- This modality is novel, and to our knowledge, has only been used clinically by our research group. In early 2020, a study was published investigating the in vitro use of SVDs in creating

PROTOCOL TITLE: Assessment of Sous Vide Water Baths for Acute Rewarming of Frostbitten Extremities.

circulating warm water baths for the rewarming of frozen pigs' feet. In this study, the SVD maintained the water bath at a constant 40°C for 30 minutes and resulted in the rewarming of the pig foot from frozen to pliable. The sous vide modality was compared against and outperformed manual water exchanges. To test this clinically, we completed a pilot study in 2021 and successfully treated acute frostbite in the ED.

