 - Dual thermometers will record water bath temperature to assess for the possibility of disequilibrium in water temperature and to detect possible hot spots.
 - The treatment will be terminated if two consecutive thermometer recordings detect water temperatures of 42°C or above.
 - The rewarming process in acute frostbite is inherently painful. Pain increases when water bath temps are above 40°C. No additional discomfort is expected beyond that for frostbite rewarming, at the target temperature of 38°C. The provider can provide analgesia as indicated. The treatment will be terminated if the patient has discomfort that is deemed by the treating provider to be above that expected from rewarming frozen tissue.
 - If treatment is discontinued prior to successful rewarming, standard rewarming will occur.
 - *Explain if any part of this study involves the use of procedures that are inconsistent with the standard of care at Dartmouth-Hitchcock Medical Center.*
 - There are no parts of the study that are inconsistent with the standard of care at DHMC. The novel treatment is to assess a treatment modality that may elevate the standard of care.
 - *All drugs and devices used in the research and the purpose of their use, and their regulatory approval status.*

PROTOCOL TITLE: Assessment of Sous Vide Water Baths for Acute Rewarming of Frostbitten Extremities.

- The ANOVA Precision® Cooker is a purpose-built device to maintain a set temperature circulating water bath. The device is not FDA approved for medical use. There will be no use of a placebo.
- The study treatment takes place entirely in the ED, which allows for comprehensive assessment of protocol compliance. If a subjects opts to discontinue participation at any time during the rewarming, standard techniques for maintaining the water bath will replace the SVD.
- *Describe randomization:*
 - All patients presenting with acutely frostbitten hands or feet will be approached for inclusion in the study. There is no randomization. Any patient not consenting to the use of the SVD but willing to allow data collection will act as a control group.
- *Prior and Concomitant Therapy:*
 - Concomitant therapies, such as intravenous fluids, anti-emetics, forced air warming blanket, and analgesia, as well as other medications deemed necessary by the provider, may be given concomitantly during the treatment period.

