14.0 Withdrawal of Subjects*

- Subjects will be withdrawn without their consent for safety reasons or medical necessity. Criteria as follows: If water bath temperatures are recorded at over 42°C on two consecutive readings during the

PROTOCOL TITLE: Assessment of Sous Vide Water Baths for Acute Rewarming of Frostbitten Extremities.

same treatment phase, if subject is judged by the treating clinician to have pain greater than expected for frostbite rewarming, or if a separate medical issue arises in the subject in which urgent treatment necessitates termination of the research.

- *Describe any procedures for orderly termination.*
 - The SVD will be powered off and the water bath maintained manually by medical staff.
- *Describe procedures that will be followed when subjects withdraw from the research, including partial withdrawal from procedures with continued data collection.*
 - Withdrawal from the research will preclude any further data collection. Data already collected at the time of the withdrawal will be analyzed with other study data but noted that the study terminated prematurely.

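### No response is prescribed for a bath reading between 40°C and 42°C, the 42°C stop is worded inconsistently, and the text conflicts on whether readings continue after 30 minutes.

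*Combined protocol and SAP*

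**What the plan says.** Section 6.0 sets the device to 38°C, and Section 3.0 gives 37-39°C as the standard-of-care range.

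**High side.** Section 6.0: "The treatment will be terminated if two consecutive thermometer recordings detect water temperatures of 42°C or above". Section 4.0: "Two consecutive temperature measurements above 42°C will prompt the cessation of the SVR". Section 14.0: "If water bath temperatures are recorded at over 42°C on two consecutive readings", with the added condition that both fall in one treatment phase.

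**Low side.** Section 15.0 moves the patient to manual rewarming if the target is not reached in 30 minutes, or if the bath stays under 37°C for more than 5 minutes.

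**Pain.** Just after the 42°C rule, Section 6.0 says: "Pain increases when water bath temps are above 40°C". It also says "The rewarming process in acute frostbite is inherently painful" and "The provider can provide analgesia as indicated", and it ends treatment for "discomfort that is deemed by the treating provider to be above that expected from rewarming frozen tissue". Section 3.0 warns that conventional methods can "burn the frostbitten and often insensate extremity".

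**Recording.** Sections 1.0 and 6.0 call for readings from both thermometers and the device every 2 minutes. The data collection text in Section 6.0 runs this to the end of the 30-minute treatment. Section 17.0 describes readings throughout the rewarming period. Section 6.0 allows a further 30 minutes if tissue is still frozen, and Section 9.0 foresees 60-90 minutes for some participants.

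**The concern.** The protocol names a temperature at which it expects more pain, yet attaches no action to a reading until the bath is about 2°C hotter. In between, the only written stop likely to respond to heat is the treating provider's view that pain exceeds what rewarming normally causes. That is a difficult call: rewarming hurts anyway, analgesia may blunt the signal, and the limb may have little sensation.

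Device control at 38°C cannot be taken for granted as the safeguard, because holding temperature is one of the primary outcomes in Section 17.0.

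The data are affected too. With 5-10 additional sites anticipated (Section 1.0), staff would probably act on a hot bath, but in different ways. The form described in Section 17.0 lists temperatures and adverse events and does not mention corrections. A bath that staff had cooled could then look like good device performance.

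Finally, the 42°C rule works only on recordings. If these stopped at 30 minutes, it would have no scheduled readings to act on in a second or third phase.

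**Working it through.** The plan has no sample size or power figure that bears on this (Section 12.0 gives none). The check sets every temperature-linked rule against the temperature scale and then the clock.

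**Rules by bath temperature**

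- Below 37°C for more than 5 minutes: stop (Section 15.0).
- 37-39°C: standard-of-care range (Section 3.0).
- Above 39°C and below 42°C: no action tied to a reading.
- Exactly 42°C on two consecutive recordings: stop under Section 6.0, no stop under Sections 4.0 and 14.0.
- Above 42°C on two consecutive recordings: stop under all three.

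The band without a reading-based action is 42 − 39 = 3°C wide. The part where the protocol itself expects more pain is 42 − 40 = 2°C wide.

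**Example.** A bath at 41°C is 41 − 39 = 2°C above the standard range and 41 − 40 = 1°C above the pain figure. At one recording every 2 minutes, a 30-minute phase has 30/2 = 15 recordings per thermometer, or 16 if time zero is counted. If the bath were at 41°C throughout, each would show it and none would meet a rule.

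**Recording after 30 minutes.** If the data collection sentence in Section 6.0 is followed literally:

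- 60-minute treatment: (60 − 30)/2 = 15 recordings per thermometer not scheduled, 30/60 = 50% of treatment time.
- 90-minute treatment: (90 − 30)/2 = 30 not scheduled, 60/90 = 67% of treatment time.

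If Section 17.0 is followed, and Section 14.0's reference to a treatment phase is read as covering later phases, both losses are zero. The text does not settle which applies.

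**Delay under the proposed step.** After a sustained crossing of 40°C, the first high recording falls 0 to under 2 minutes later and the second 2 to under 4 minutes later. Staff would therefore act 2 to under 4 minutes after the crossing.

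**The case against.** The strongest reply is that nothing in the documents makes 40°C a safety limit. Section 6.0 links it to pain, not injury, and answers pain with analgesia and a discomfort stop. The bench study in Section 3.0 ran at a constant 40°C for 30 minutes, and Section 15.0 reports no adverse events in the pilot. Other safeguards exist: a researcher at the bedside, two thermometers placed partly to find hot spots, continuous temperature assessment (Section 15.0), a biomedical engineering review that rated the device low risk, the patient's right to stop, and a study hold after one unanticipated event possibly due to the device (Section 18.0). Staff are trained in managing the bath (Section 24.0), and the attached forms are not visible.

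Much of this stands. A reader might infer that an overheated bath would go unnoticed. It would not: it would be seen at the next 2-minute recording. What is missing is a prescribed response. A reader might also make much of the stops lying 42 − 38 = 4°C above the set point but only 38 − 37 = 1°C below it. The low-side rule guards against delayed treatment and the high-side rule against overheating, so the margins need not match.

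The reply does not close the gap. In the visible text, no listed safeguard says what to do when a thermometer reads 41°C. Nor does the reply touch the mismatch at 42°C or the conflict over later recordings.

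**Conclusion.** The point holds as a gap in the prescribed response, with two inconsistencies that weaken the existing stop. A bath between 40°C and 42°C could run a full session with no temperature rule met, only a provider-judged pain stop behind it.

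Its importance is minor to moderate. Three stronger conclusions might be drawn, and the documents support none of them:

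- That the 42°C stop is wrong, or that 40-42°C burns. Section 15.0 names hot water burns as a hazard without giving a temperature.
- That overheating is likely. No overshoot rate is given, so the figures above describe what the rules cover, not how often it would matter.
- That the 42°C rule certainly has no readings after 30 minutes. Sections 14.0 and 17.0 imply that recording goes on; the 50% and 67% apply only on the literal reading of one sentence.

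The finding covers the protocol text only; the forms or training material may contain a response. Using 40°C as the trigger assumes that the protocol's own pain figure is a sensible point for a check. The exact threshold is a clinical choice.

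**What to change.** 1. Keep the 42°C stop and use the at-or-above wording in Sections 4.0, 6.0 and 14.0.
2. In Section 6.0, record both thermometers and the device every 2 minutes in every 30-minute phase until rewarming is complete.
3. In Section 6.0, add a step: if either thermometer reads above 40°C at two consecutive recordings while the limb is in the bath, the researcher checks the bath and limb and notifies the treating provider, who decides whether to correct the bath or stop the device. The researcher logs the excursion and any correction. Do not list this as a withdrawal criterion in Section 14.0, where withdrawal ends data collection; the rewarming result would be lost.
4. In Section 17.0, report excursions descriptively and report readings after a correction separately. Do not define each excursion as a primary-outcome failure: a single probe near the heater could decide it.

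The cost is a few sentences and extra rows on the data sheet, with no new equipment. One thermometer sits nearest the heater, so some checks will prove unneeded. Readings after a correction will not show unaided device performance, which is why they are reported separately.
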